### **i. Data Management**

Data will be maintained in the Prisma Health REDCap and on a secure server with password protection. Study data and signed consent documents will be stored in a locked office in Prisma Health Orthopedics. Only authorized research members of this study can access this information. The researchers involved in this study commit to handle all information with care and to protect research subjects' identities. Study data will be de-identified after data collection and before sending to the biostatistician for data analysis. No PHI data will be published or presented.

Key data points include:

- BMI
- Demographic info (age, gender, race, ethnicity)
- ABI
- Hb-A1c
- Diabetes mellitus diagnosis
- Wound characteristics such as size, exudate amount, and tissue type (as documented by PUSH Tool 3.0) and Wagner stage
- Lab results (CMP, lipid panel, INR/PT)
- ECG results
- Plantar pressure profile readings
- Clinical photos of wound
- Current medications (throughout study participation)
- Treatment received as standard of care
- Rate of infection
- Rate of surgical intervention
- Rate of amputation
- Rate of ulcer recurrence
- Comorbidities
- VAS scores
- Compliance with supplementation
- Supplementation side effects

### **j. Confidentiality**

Signed consent documents will be stored in a locked office at Prisma Health Orthopedics. Data will be maintained in the Prisma Health REDCap and on a secure server with password protection. Only authorized research members of this study can access this information. The researchers involved in this study commit to handle all information with care and to protect research subjects' identities. Study data will be de-identified after data collection and before sending to a biostatistician for data analysis. No PHI data will be published or presented.

### **k. Withdrawal of Subjects**

Subjects may withdraw from the study at any time. All data recorded to that point may be kept and used for data analysis.

The provider has the authority to remove any subject from the study at his/her discretion, at which time the provider will inform the subject of withdraw. Circumstances for withdraw include, but are not limited to:

- a. Failure to meet inclusion/exclusion criteria (labs, A1c, ECG parameters)
- b. Lack of compliance with supplementation
- b. Rapid progression of wound(s) which is expected to result in surgery during the 6-week study period
- c. Severe adverse effects which are possibly related to supplementation

All data recorded to the point of withdraw may be kept and used for data analysis.

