## 2) Objectives / Research Aims

Chronic, non-healing foot ulcers are a common complication of diabetes that can threaten loss of limbs, shorten life expectancy, and require resource-intensive treatment. Patients who exhibit these late effects of diabetes are often medically complex and have not only a shortened life expectancy but also a lower quality of life than their non-ulcer peers. Despite the prevalence of obesity in these patients, many exhibit metabolic signs of malnutrition, malabsorption, or both. Even when direct treatment for the ulcer is ideal, if the patient does not have the metabolic building blocks or the correct macronutrient healing environment, then treatment will be futile.

To this end, we believe focused immunonutrition supplementation consisting of L-Arginine, Omega-3 fatty acids, and Vitamin C combined with quality wound care will lead to an improvement in treatment success, satisfaction, patient reported outcome measures, and limb salvage.

**Specific Aim 1:** To compare the healing process of diabetic patients with chronic, non-healing, lower-extremity wounds receiving oral immunonutrition supplementation to patients receiving traditional care.

- a. This will be addressed by performing a prospective, randomized pilot study including 30 diabetic patients with chronic lower extremity wounds, Wagner stages 1-2. Fifteen patients will receive oral immunonutrition supplementation (2 grams omega-3 fatty acids + 500 mg vitamin C + 4.5 grams L-arginine per day) in addition to current standard of care and 15 patients will receive the current standard of care only. Study participation will continue for 6 weeks.
- b. Effect of wound healing will be assessed utilizing the Pressure Ulcer Scale for Healing (PUSH) Tool 3.0 which scores ulcers based on size ( $\text{cm}^2$ ), exudate amount, and tissue type present. Plantar pressure profiles will be recorded using a Tekscan Pressure Mat and plantar weight-bearing foot images will be recorded. Additionally, patient charts will be monitored over the course of the study to identify rate of infection, surgical intervention, and amputation and for one year following completion of the study to assess ulcer recurrence rates.

**Specific Aim 2:** To assess compliance and patient satisfaction with an oral immunonutrition supplementation regimen in diabetic patients with chronic, non-healing, lower-extremity wounds.

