**e. Study Endpoints**

Primary Outcome: Complete wound closure of a chronic, non-healing wound at 6 weeks.

- a. Complete wound closure will be defined as skin reepithelialization without drainage or dressing requirements confirmed at two consecutive study visits 2 weeks apart. Incidence of complete wound closure in the control group will be compared to that of the treatment group.

Secondary Outcome: Rate of wound closure over 6-week study period.

- a. PUSH Tool 3.0 scores and clinical photos will be compared between the control group and treatment group to evaluate the rate of wound closure over the course of the 6-week study period.

Tertiary Outcome: Compliance and patient satisfaction with immunonutrition supplementation regimen.

- a. Patient satisfaction surveys and compliance logs will be evaluated to assess feasibility of implementing an immunonutrition regimen into standard wound care.

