  - a. If randomized to the control group (SOC only), patients will receive standard of care defined as sharps debridement, appropriate dressing, and offloading. If randomized to the treatment group (SOC + Immunonutrition), subjects will receive standard of care defined as sharps debridement, appropriate dressing, and offloading in addition to a 6-week supply of Omega-3 fatty acids (soft gel form, 2 pills per day, total of 1.68 grams) and L-Arginine/Vitamin C (powder form, to be mixed with 8 oz liquid, 1 scoop once daily, total of 4.5 grams L-arginine and 500 mg vitamin C). Subjects will also be provided a compliance log with detailed instructions for taking and tracking supplements.
5. Patients will be scheduled for biweekly wound checks with their provider (weeks 2, 4, 6). Wound characteristics will be documented at each follow up visit using the PUSH Tool 3.0, images of the wound will be obtained, and an interval history and physical exam will be documented. The provider will verify and document concomitant medications in the patient's chart. The provider will visualize and evaluate any additional wounds that are present (new or present at time of enrollment) and record characteristics in the patient's chart. Patients will complete a questionnaire detailing their pain level (VAS), symptoms experienced during the treatment phase, and any unscheduled visits to emergency departments/urgent care centers. This will be completed via a paper survey in clinic during their office visit (Appendix 4). On weeks where an office visit is not scheduled (weeks 1, 3, 5), a research coordinator will call the patient and collect survey responses (Appendix 3).
6. At the final office visit (week 6), plantar pressure profiles will be recorded via the Tekscan Pressure Mat, and clinical plantar weight-bearing images will be captured. Patients randomized to receive the oral immunonutrition supplementation will complete an additional survey detailing their satisfaction with the treatment plan and any additional thoughts they would like to share (Appendix 5) and return the completed compliance log

(Appendix 6). Patients in the treatment arm will have CMP and lipid panel labs drawn at this timepoint or within 3 months of study completion.

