## **Appendix 5: Patient Satisfaction/Completion Survey**

### **Effects of Supplemental Immunonutrition on Healing of Chronic Non-Healing Lower Extremity Ulcers in Diabetic Patients: Completion Survey**

\*This survey should only be completed at the 6-week follow-up visit if you received the immunonutrition supplementation as a part of the research study\*

Name: \_\_\_\_\_ Date: \_\_\_\_\_

1. How satisfied were you with the immunonutrition therapy?  
 Very Unsatisfied  
 Unsatisfied  
 Neutral  
 Satisfied  
 Very Satisfied
  
2. Would you choose to follow the same therapy plan again, if you were to develop another foot ulcer?  
 Yes  
 No
  
3. Would you recommend this therapy to friends/family?  
 Yes  
 No
  
4. Do you feel the therapy aided in the healing of your ulcer?  
 Yes  
 No
  
5. How would you rate the difficulty in taking the supplementation?  
 Very Difficult  
 Somewhat Difficult  
 Neutral  
 Easy  
 Very Easy
  
6. How often did you forget to take the supplementation?  
 Never  
 Sometimes  
 Often  
 Almost Always
  
7. Did you experience any negative side effects from the supplementation therapy?  
 Yes, please explain: \_\_\_\_\_  
 No
  
8. Is there anything else you would like us to know about your experience with this therapy?  
\_\_\_\_\_

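### Non-compliance is a listed ground for removal from the study, and the log and satisfaction survey are collected only at week 6, so Aim 2 feasibility may be overstated to the extent that this ground is used

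*Combined protocol and SAP*

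**What the plan says.** Section 2 states Specific Aim 2 as: "To assess compliance and patient satisfaction with an oral immunonutrition supplementation regimen". Section 6.e makes this the tertiary outcome and names its data sources: "Patient satisfaction surveys and compliance logs will be evaluated to assess feasibility of implementing an immunonutrition regimen into standard wound care".

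Section 6.k says: "The provider has the authority to remove any subject from the study at his/her discretion". Its list of example circumstances is open-ended and includes "Lack of compliance with supplementation". No level of non-compliance is given. The removal is from the study, not just from the supplement. The section also says: "All data recorded to the point of withdraw may be kept and used for data analysis".

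Section 6.f, step 6, has supplement patients complete the satisfaction survey at the final (week 6) office visit "and return the completed compliance log". The Visit 3 list in 6.f and Appendix 1 agree. The survey form in Appendix 5 carries the instruction: "This survey should only be completed at the 6-week follow-up visit if you received the immunonutrition supplementation".

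Compliance is also reviewed at each weekly contact. The phone script (Appendix 4) asks whether the supplement has been taken daily and, if not, why. The clinic form (Appendix 3) asks about difficulty in taking it.

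Section 6.h contains no analysis of compliance or satisfaction. It gives no definition of compliance, no denominator for Aim 2 and no rule for withdrawn patients.

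**The concern.** The quantity being measured is itself a permitted reason to stop measuring it. Take a patient who gives up the powder in week 2 because it is hard to take. The provider may withdraw that patient, who then never reaches the visit at which the log is handed in and the survey completed. Yet that patient's experience is what a feasibility assessment most needs.

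Feasibility is one of the main things a 30-patient pilot can deliver. With 15 patients on the supplement, each withdrawal takes 1/15 = 6.7% of the arm, so one or two removals can change the message.

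There is a second consequence. Controls have no supplement to comply with, so this ground can operate only in the supplement arm. Closure at 6 weeks must be confirmed at two consecutive visits two weeks apart (6.e), so a patient withdrawn early may have no assessable primary outcome. Section 6.h does not say how such a patient is handled.

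**Working it through.** The documents state no compliance rate, feasibility threshold or dropout rate, so there is no figure of the plan to reproduce. The check has two parts.

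**1. What is left for a patient removed before week 6**

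- *Log (Appendix 6):* the only dose-by-dose record. The patient holds it and returns it at week 6. Section 6.k keeps only data already recorded at withdrawal, and no step retrieves the log at an early exit.
- *Weekly items (Appendices 3 and 4):* available up to removal. One is a yes/no answer with a reason, the other concerns difficulty. Neither counts doses, and 6.e does not name them as a source for the feasibility outcome.
- *Satisfaction:* nothing. The weekly items do not ask about it, and the one survey is scheduled for week 6.

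**2. Size, by illustration**

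Inputs: 15 supplement patients (Section 2). The number of true compliers c, the number of non-compliers removed w, and the satisfaction rates are assumptions. The calculation also assumes that only patients who return a week-6 log are analysed.

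- All assigned patients: c/15
- Completers only: c/(15 − w)

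| True compliance | Removed (w) | Completer-based rate | Overstatement |
|---|---|---|---|
| 12/15 = 80% | 0 | 12/15 = 80% | 0 |
| 12/15 = 80% | 1 | 12/14 = 86% | 5.7 points |
| 12/15 = 80% | 2 | 12/13 = 92% | 12.3 points |
| 12/15 = 80% | 3 | 12/12 = 100% | 20.0 points |
| 10/15 = 67% | 1 | 10/14 = 71% | 4.8 points |
| 10/15 = 67% | 3 | 10/12 = 83% | 16.7 points |
| 10/15 = 67% | 5 | 10/10 = 100% | 33.3 points |
| 8/15 = 53% | 1 | 8/14 = 57% | 3.8 points |
| 8/15 = 53% | 7 | 8/8 = 100% | 46.7 points |

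Mean intake behaves the same way. Suppose 12 patients take 95% of doses and 3 take 40%. The true mean is (12×95 + 3×40)/15 = 84%. With two of the three removed it is (12×95 + 40)/13 = 90.8%. With all three removed it is 95%.

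For satisfaction, assume that 80% of compliers and 20% of non-compliers are satisfied. Over all 15 patients the expected rates are:

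- c = 12: (12×0.8 + 3×0.2)/15 = 68%
- c = 10: (10×0.8 + 5×0.2)/15 = 60%
- c = 8: (8×0.8 + 7×0.2)/15 = 52%

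If every non-complier is removed before week 6, the survey shows 80% in each case.

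Reporting over all 15, with removed non-compliers counted as non-compliant, restores c/15. For 12/15 the exact 95% interval is 52% to 96%.

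**The case against.** The best defence has four parts.

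- *Withdrawal is discretionary.* Section 6.k permits removal but does not require it. Poor compliers may all stay, and the bias from this rule is then zero. This stands, and it limits the size. It does not change the direction for compliance, because removing non-compliers can only raise the rate. With no threshold, the size also cannot be known in advance.
- *Compliance is captured weekly and earlier data may be used.* This stands in part. A patient who stops in week 2 should be picked up, with a reason, at the next contact if still in the study, and Section 6.i lists compliance as a key data point. But these items are coarse, and they do nothing for satisfaction.
- *No completer-only analysis is stated.* This is correct. The Aim 2 denominator is undefined, so the percentages above show what happens if the gap is filled with week-6 returns.
- *The Appendix 5 instruction may only limit the form to supplement recipients.* That reading is possible. On either reading, no collection at early exit is specified.

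A reader might go further and infer that compliance is overstated by construction. The documents do not support this, since removal is optional and the analysis set is open. A reader might also infer that the healing comparison becomes compliant supplement patients against all controls. The text does not say so. Poor compliers need not be removed, other grounds such as rapid wound progression can apply to controls, and wound data recorded before withdrawal may be used.

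**Conclusion.** The point holds as a conditional one. A stated rule, not just missing detail, allows poor compliers to be removed from the study that is meant to measure compliance. The dose-level log and the satisfaction survey would then probably be missing for them. The satisfaction part is the stronger, because nothing else in the plan records satisfaction. The compliance part is partly mitigated.

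With true compliance assumed at 12/15, one to three removals followed by a completer analysis give an overstatement of 5.7 to 20 points; with no removals it is zero. The upward direction for satisfaction assumes that removed patients are less satisfied than those who stay.

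For healing, the supportable statement is narrower: removals on this ground can occur only in the supplement arm, so week-6 outcomes may be lost from that arm alone. This should be corrected, because data not collected when a patient leaves may not be recoverable.

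**What to change.** - *Section 6.k:* delete non-compliance as a ground for withdrawal, and state that non-compliance alone is not a reason to remove a patient from study follow-up. The explicit statement is needed because the list is open-ended, so deletion alone would leave the provider's discretion unchanged. These patients stay on the existing visits and calls through week 6 and in the healing analysis as randomised. Whether they continue the supplement remains with the provider. Section 9 already separates the two for qualifying adverse events, where the supplement stops and monitoring continues.
- *Section 6.f, step 6, and Appendix 5:* have the log returned and the survey completed at week 6, or at the last contact if the patient leaves early.
- *Section 6.h:* define compliance (for example, the share of the 42 days' doses taken) and report it over all patients randomised to supplementation. Count days after a patient's own decision to stop as not taken. Report protocol-directed stops (adverse events, preparation for surgery) separately with reasons, so that safety-driven stops are not scored as poor compliance.

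The cost is a short amendment, an instruction line on the survey form and a brief analysis paragraph. No visits are added. Reported compliance may look less favourable.

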#### **h. Statistical Analysis**

Summary statistics will be used to summarize measurements and assessed for unadjusted differences across treatment condition. Student's t-tests will be used for continuous measures, exact binomial tests for dichotomous measures, and chi-square tests for categorical measures.

The main outcome of interest is the proportion of wound closed at the end of 6 weeks which we will model in a generalized linear models framework

$$E[g(y_i)] = \beta_0 + Trt_i\beta_1 + Z_i\gamma$$

where  $y_i$  is the outcome measure of interest of the  $i$ th participant,  $Trt_i$  is an indicator variable of whether the participant was assigned to the treatment condition,  $Z_i$  is a vector of covariates for which we will adjust the model (i.e., initial wound size, diabetes etiology, sex, race, and age), and  $\gamma$  is a vector of regression parameters. We have written the outcome in terms of a link function ( $y_i$ ) to emphasize that we will estimate a linear regression model (identity function) as well as a zero-one augmented beta regression model for which we will choose from among several link functions (logit, log, log-log, and complementary log-log). Anticipating that we will have outcomes of exactly 0% or 100% reduction of the wound size, we will model the transformed outcome

$$y_i^* = \frac{99y + 0.5}{100}$$

Our focus is on the null hypothesis  $H_0: \beta_1 = 0$ . We will evaluate this null hypothesis using a Wald test of the parameter based on an appropriate variance estimate – chosen from model-based, sandwich, or sandwich based on an evaluation of the implied dispersion properties of the model-based variance estimator.

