Other secondary outcome variables to be modeled include the time to complete healing (Cox proportional hazards regression), rate of closure (Cox proportional hazards regression), presence of infection (binary regression), and need for surgery (binary regression). Cox proportional hazards models will be used to interpret the relative hazards between treatment conditions. The proportional hazards assumption will be checked using Schoenfeld residuals and accelerated failure time (parametric) regression models will also be evaluated. Binary outcomes will be modeled using various link functions (logit and log). Exponentiated coefficients for logit-link models will be interpreted as odds ratios, and exponentiated coefficients from log-link models will be interpreted as risk ratios. Binary outcomes may be relatively rare, and so we will also

estimated binary models using exact statistics. In addition, we will investigate bias through estimation of bias-corrected models.

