**Plan for management of unplanned and/or emergent surgery:**

If a wound of a patient enrolled in the treatment arm is progressing more rapidly than expected, as determined by the wound care provider, the provider will withdraw the patient and instruct them to discontinue supplementation immediately in preparation for surgery. Additionally, all patients will be flagged as participating in this research study in EPIC with details on the supplements involved. There will be an explicit note that the PI of the study should be contacted prior to any surgical procedure to discuss the timing of the surgery and discontinuation of the supplements. If it is not possible for the patient to discontinue the supplementation 2 weeks prior to surgery, all relevant parties (PI, surgeon, anesthesia) will be notified of the patient's involvement in the study and discuss additional potential risks of surgery and a patient-specific strategy for management of these risks. The study coordinator will review the charts of patients included in the supplement arm daily and will facilitate this communication between parties, if necessary.

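### The withdrawal rules can leave week-6 wound outcomes missing unequally between the arms, for reasons tied to treatment or outcome, and nothing secures a wound assessment after removal

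*Combined protocol and SAP*

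**What the plan says.** Section 6.k (Withdrawal of Subjects) gives a general power: "The provider has the authority to remove any subject from the study at his/her discretion". Its list of circumstances is open-ended. Two entries concern the supplement: "Lack of compliance with supplementation" and "Severe adverse effects which are possibly related to supplementation". A third, rapid wound progression expected to lead to surgery within the six weeks, is not limited to one arm. On data, the section says: "All data recorded to the point of withdraw may be kept and used for data analysis".

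The surgery plan in section 9 is worded differently. It opens "If a wound of a patient enrolled in the treatment arm is progressing more rapidly than expected" and continues that, on the wound care provider's judgement, "the provider will withdraw the patient and instruct them to discontinue supplementation immediately in preparation for surgery". It has no corresponding instruction for controls.

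Also in section 9, the adverse event paragraph has treatment-arm patients with an event of Grade 3 or above (Grade 2 or above for bone marrow and cardiovascular events) stop the supplement. They are then monitored until the event resolves or stabilizes.

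Section 6.e makes complete closure at 6 weeks the primary outcome, confirmed at two consecutive visits two weeks apart. Section 6.h says "The main outcome of interest is the proportion of wound closed at the end of 6 weeks". Section 6.f schedules wound checks at weeks 2, 4 and 6. Section 6.h names no analysis population and gives no rule for a missing outcome.

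**The concern.** Controls receive standard care without a supplement, so they can neither fail to comply with it nor have an adverse effect from it. Rapid progression is close to the opposite of the primary outcome, and the plan treats it differently by arm: withdrawal is required in one and optional in the other. The section 9 trigger is also looser (faster than expected, against expected to result in surgery within six weeks).

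A patient removed early has no week-6 value unless someone collects one, and the plan does not ask for that. The primary comparison may then no longer cover everyone randomized, and the missing patients would differ between arms for reasons linked to treatment or healing. The Cox model for time to healing can censor at removal, but censoring because a wound is deteriorating is informative.

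Two other outcomes are touched in part. The satisfaction survey is completed and the compliance log returned at week 6, so a patient removed earlier gives no survey and perhaps no log. Surgery or amputation after withdrawal is not clearly captured either.

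**Working it through.** **Step 1: what the text does in each arm**

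| Ground | Supplement arm | Control arm |
|---|---|---|
| Non-compliance with supplement (6.k) | removal allowed | cannot arise |
| Severe adverse effect possibly related to supplement (6.k) | removal allowed; section 9 instead stops the supplement and monitors | cannot arise |
| Rapid wound progression | withdrawal required (section 9) | removal allowed only (6.k) |
| Other provider discretion (6.k) | allowed | allowed |

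In the surgery plan, withdrawing the patient and telling them to stop the supplement are two separate acts, and 6.k lists rapid progression as a reason to leave the study. The natural reading of withdrawal there is therefore from the study, not only from the supplement.

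**Step 2: what is lost**

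- Proportion of wound closed at week 6: not measured if removal comes before week 6.
- Confirmed closure: needs two visits two weeks apart out of weeks 2, 4 and 6. Removal before the week 4 visit makes it impossible. Removal between weeks 4 and 6 leaves it only if the wound was closed at both weeks 2 and 4.
- Chart monitoring (6.f) runs during participation and then for one year for recurrence. It is not said to continue for removed patients or to capture week-6 closure.

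**Step 3: size.** The plan has no figure to reproduce. From the documents: 15 patients per arm (6.c). Assumed: all closure rates, wound means and removal counts, and that removed patients are left out of the analysis.

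*Closure, true result 5/15 = 33.3% in both arms, k supplement patients left out.* Rate among those remaining: 5/(15-k) if the removed would not have closed, (5-k)/(15-k) if they would have.

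| k | Removed would not have closed | Shift (points) | Removed would have closed | Shift (points) |
|---|---|---|---|---|
| 1 | 5/14 = 35.7% | +2.4 | 4/14 = 28.6% | -4.8 |
| 2 | 5/13 = 38.5% | +5.1 | 3/13 = 23.1% | -10.3 |
| 3 | 5/12 = 41.7% | +8.3 | 2/12 = 16.7% | -16.7 |

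Standard error of the difference: sqrt(2 × 0.333 × 0.667 / 15) = 0.172, about 17 points.

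*Proportion of wound closed, k = 2 progressing wounds at 0%, the other 13 averaging m.* Full-arm mean = 13m/15.

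- m = 60%: 52.0%, so leaving the two out adds 8.0 points.
- m = 40%: 34.7%, adds 5.3.
- m = 80%: 69.3%, adds 10.7.

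*False-positive rate.* Full enumeration of two Binomial(15, p) arms with equal p, leaving out up to three supplement non-closers, two-sided 0.05. The uncorrected chi-square and Fisher tests stand in for the planned models.

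| p | Chi-square, k=0 | Chi-square, k=3 | Fisher, k=0 | Fisher, k=3 |
|---|---|---|---|---|
| 0.2 | 5.0% | 7.2% | 1.7% | 3.4% |
| 0.3 | 5.5% | 9.3% | 1.7% | 4.5% |
| 0.5 | 4.6% | 13.9% | 1.7% | 9.0% |

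With one removal the effect can be small: chi-square 5.6% at p = 0.3.

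**Step 4: what bounds would show.** Each missing patient widens the range for an arm's closure rate by 1/15 = 6.7 points. With 5 closed among 13 assessed and two missing, the range is 5/15 = 33.3% to 7/15 = 46.7%.

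**The case against.** Several points on the other side stand, and they limit the claim.

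- **The loss is unequal, not strictly one-sided.** A reader might infer that only supplement patients can be lost. Section 6.k covers any subject, is open-ended, and includes rapid progression for controls.
- **Surgery is not simply lost.** A reader might infer that treatment-arm surgery would go unrecorded. With two true cases per arm, that would give 0/13 = 0% against 2/15 = 13.3%. The documents do not support this as an expected result. The secondary outcome is the need for surgery, which is likely known when a patient is withdrawn in preparation for it and can fall within the data kept. The figure also assumes no control facing surgery is removed. It is a worst case; only later surgery or amputation is in real doubt.
- **Compliance is not wholly lost.** Supplement use is reviewed at each weekly contact (section 6.f; phone and clinic surveys), and reviews before removal are kept.
- **Severe adverse events need not lead to removal.** The section 9 rule stops the supplement only, and such patients by default stay on the visit schedule. This is a fair point, but it leaves section 9 in conflict with the 6.k ground.
- **The bias depends on an analysis the plan does not state.** Nothing says removed patients are excluded. The treatment indicator in 6.h follows assignment, and permission to keep earlier data does not forbid later collection. Biweekly visits are described as standard care, so some wound status may reach the chart.

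The last point does not dispose of the matter. A regression on week-6 outcome cannot use a patient without a value unless a rule supplies one, and chance chart entries are not a planned assessment. The small size of a pilot does not help either: systematic loss is not sampling noise, and its rates may inform a larger trial.

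**Conclusion.** The concern holds as a matter of stated rules, not mere silence. Sections 6.k and 9 allow or require study withdrawal on grounds that fall unequally on the arms and relate to treatment or outcome, and no week-6 wound assessment is secured afterwards.

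The size cannot be estimated from the documents. Under the assumptions shown, one to three omitted supplement patients move the closure difference by +2.4 to +8.3 or by -4.8 to -16.7 points. Two omitted progressing wounds raise the mean proportion closed by 5.3 to 10.7 points. The closure shifts lie within the standard error of about 17 points.

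A reader might infer that the net bias favours the supplement. That is plausible for removals due to progression, but the direction for non-compliance and adverse effects is uncertain, so no overall direction can be claimed. The change should be made while patients are still being followed, since assessments not made cannot be recovered at analysis.

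**What to change.** In section 6.k and the section 9 surgery plan:

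1. Replace study removal for supplement-related adverse effects, non-compliance and rapid wound progression with discontinuation of the supplement. Use the section 9 adverse event trigger and keep the pre-surgery stop.
2. Continue the scheduled wound assessments through week 6, under the same rule in both arms, unless the patient withdraws consent.
3. Record both the need for surgery and any surgery or amputation performed. Count a study ulcer operated on or amputated before week 6 as not closed. Other conventions are possible, but one should be fixed in advance.
4. State in section 6.h that patients are analysed in their assigned arm. Where closure is still missing, report the comparison with missing counted as not closed and again as closed.

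The cost is a few sentences and some follow-up of patients who are off supplement. The visits are already scheduled in section 6.f, and section 12 describes them as standard care billable to insurance. No safety action is weakened.
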